### 5.3.2 Dose Escalation Rules and Definition of MTD

In Stage 1, each subject will be assigned to Dose Level 1 (40 mg/dose BID), Dose Level 2 (80 mg/dose BID), or Dose Level 3 (100 mg/dose BID) sequentially according to the dose level being explored at the time of subject enrollment. A Dose Level -1 (20 mg/dose BID) is provided in case a subject assigned to Dose Level 1 (40 mg/dose BID) requires dose reduction. In Stage 2, 8 subjects were enrolled at the Stage 1 MTD, Dose Level 2 (100 mg/dose BID). In Stage 3, each subject will be assigned to Dose Level 6 (160 mg/dose TID), or Dose Level 7 (200 mg/dose TID) sequentially according to the dose level being explored at the time of subject enrollment. Dose Level 5 (120 mg/dose TID) is provided in case a subject assigned to Dose Level 6 (160 mg/dose TID) requires dose reduction. Dose Level 4 (100 mg/dose BID) is provided in case a subject assigned to dose Level 5 (120 mg/dose TID) requires dose reduction.

During the study, dose escalation will depend on evaluations of safety in cycle 1 of therapy. The following dose escalation rules will be employed:

- Three subjects will be studied at the first dose level. If none of these three subjects experience DLT during cycle 1, then the dose will be escalated to the next higher level in the three subsequent subjects.
- If one of three subjects experiences DLT at the current dose during cycle 1, then three more subjects will be accrued at the same dose. If none of these three additional subjects experience DLT during cycle 1, then the dose will be escalated in subsequent subjects. If one or more of the three additional subjects experiences DLT in the first cycle, the MTD has been exceeded and three more subjects will be treated at the next lower dose (if only three subjects were previously treated at that prior dose).
- If two or more subjects experience DLT in the first cycle, then the MTD has been exceeded and three more subjects will be treated at the next lower dose level (if only three subjects were previously treated at that prior dose).
- No intrasubject dose escalations in subsequent cycles of therapy will be permitted.

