At the first and at all subsequent dose levels, each group of three subjects within a cohort must be observed for a minimum period of at least 28 days without DLT before subsequent subjects are enrolled at the next dose level. Escalation to the next dose level can occur with the concurrence of the Protocol Chair, AMC Group Statistician, and the AMC Medical Monitor upon review of the safety data from the ongoing group of three subjects. The PTC medical monitor should be notified promptly of the dose escalation decision.

The establishment of an MTD will be based on a review of the overall first-cycle safety data by the Protocol Chair, AMC Group Statistician, and the AMC Medical Monitor. The MTD is the starting dose level at which 0/6 or  $\leq 1/6$  subjects experience DLT with the next higher dose having at least 2/3 or 2/6 subjects encountering DLT during the first treatment cycle. Effectively, the Stage 1 MTD is that dose associated with first-cycle DLT in  $< 33.3\%$  of subjects. If none of the dose levels tested is associated with 2/3 or 2/6 subjects experiencing DLT during the first treatment cycle, subjects in the Stage 2 (Section 5.3.5) of the study will be treated at a dose of 100 mg/dose BID. Similarly, in Stage 3, if neither of the 2 dose levels (160 mg/dose TID nor 200 mg/dose TID) tested is associated with at least 2/3 or 2/6 subjects experiencing DLT during the first treatment cycle, subjects in the expansion cohort will be treated at a dose of 200 mg/dose TID.

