When there is a dose modification, the subject should be notified of the change in dose and the appropriate clinic staff should instruct the subject about the revised number of study medication capsules to be used per dose according to the new dose level.

Clinical use of other anti-VEGF compounds (e.g., bevacizumab) can be associated with delayed wound healing. For this reason, subjects who require surgery or a deep invasive procedure should have PTC299 held for  $\geq 2$  weeks before the procedure, if possible, and PTC299 should be held for  $\geq 2$  weeks after the procedure, or until complete wound healing, to avoid the theoretical risk of impaired wound closure.

#### 5.3.5 Treatment in Phase 2

Once the safety profile at each dose level has been established based on first cycle DLTs in Phase 1, up to 21 additional subjects whose response to treatment can be evaluated will be enrolled in the Phase 2 portion of the study at the highest safely tolerated dose established in the Phase 1 portion to better define the safety, antitumor activity and biological activities of PTC299 at this dose level. In the Phase 2 portion of the study, Simon's 2-stage design will be used, as described in Section 11.1. Treatment will consist of 4 week cycles of therapy (56 or 84 doses) as described in Section 5.3.2. The maximum duration of treatment is 12, 4-week cycles. Definitions of DLT will be as described in Section 5.3.3. Study drug interruptions and dosage reductions will be managed as described in Sections 5.3.1 and 5.3.4.

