**Table 6. Probability of Dose Escalation within Stage (Stage 1 & Stage 3)**

True Incidence of DLT	Probability of Escalating
10%	0.91
20%	0.71
30%	0.49
40%	0.31
50%	0.17
60%	0.08

Abbreviations: DLT = dose-limiting toxicity

Thus, if the true underlying proportion of DLTs is 20% at the current dose level, there is a high probability (0.71) of dose escalation to the next dose level. Conversely, if the true underlying proportion of DLTs is 50% at the current dose level, there is a low probability (0.17) of escalation to the next dose level.

In the Phase 2 portion of the study, Simon's 2-stage design is used to test the null hypothesis that the response rate (CR + PR) is  $\leq 10\%$  against the alternative that it is  $35\%$  at the one-sided 0.05 significance level with power of 0.90. Eleven subjects will be enrolled at the first dose level administered in Phase 2 (eg, 100 mg/dose BID) considering subjects from both the Phase 1 and Phase 2 portions of the study. If  $\leq$  one out of 11 subjects respond, the study will be stopped. If  $\geq$  two out of 11 subjects respond, the study will enroll 18-21 additional subjects in Stage 3. Assuming that the true response rate is  $\leq 10\%$ , the probability of stopping the trial at the end of Stage 2 is 0.697. However, if the true RR is  $\geq 35\%$ , then there is only a probability of 0.059 that the trial will be stopped erroneously in Stage 2.

Using the proposed dose escalation scheme from 100 mg/dose BID to 160 mg/dose TID, the probability of dose escalation based on the true rate of DLT at the lower dose, is given in Table 7 below:

**Table 7. Probability of Dose Escalation  
(100 mg/dose BID to 160 mg/dose TID)**

True Incidence of DLT	Probability of Escalating
10%	0.96
20%	0.82
30%	0.59
40%	0.35
50%	0.18
60%	0.08

Abbreviations: DLT = dose-limiting toxicity

Thus, if the true underlying proportion of DLTs is 20% at the 100 mg/dose BID dose level, there is a high probability (0.82) of dose escalation to the next dose level. Conversely, if the true underlying proportion of DLTs is 50% at the 100 mg/dose BID dose level, there is a low probability (0.18) of escalation to 160 mg/dose TID.

At the end of Stage 3, if  $\geq 6$  subjects respond, then the null hypothesis that the true response probability is  $\leq 10\%$  will be rejected, and further investigation of PTC299 in this patient population is warranted.

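### Table 7's probabilities of escalating from 100 mg BID to 160 mg TID belong to a rule the protocol does not state; the written 3+3 scheme gives values up to 0.11 lower

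*Combined protocol and SAP*

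**What the plan says.** Section 5.3.2 contains the only dose escalation rule. It is introduced for the whole trial: "During the study, dose escalation will depend on evaluations of safety in cycle 1 of therapy". With 0/3 DLTs the dose goes up. With 1/3, three more subjects are added and the dose goes up only if none of them has a DLT. Otherwise: "If one or more of the three additional subjects experiences DLT in the first cycle, the MTD has been exceeded". A further bullet says: "If two or more subjects experience DLT in the first cycle, then the MTD has been exceeded".

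The same section requires agreement by three roles: "Escalation to the next dose level can occur with the concurrence of the Protocol Chair, AMC Group Statistician, and the AMC Medical Monitor". It also glosses the target, saying that "the Stage 1 MTD is that dose associated with first-cycle DLT in" under 33.3% of subjects.

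Section 11.1 gives two tables of escalation probabilities. Table 6 covers steps within Stage 1 and within Stage 3. Table 7 covers the step between stages and is introduced by "Using the proposed dose escalation scheme from 100 mg/dose BID to 160 mg/dose TID". The text after it reads 0.82 at 20% true DLT as high, and at 50% says "there is a low probability (0.18) of escalation to 160 mg/dose TID".

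Sections 3.3.1 and 11.1 report that Stage 1 enrolled three subjects at each of three doses and that Stage 2 enrolled eight more at 100 mg BID, making 11 at that dose. For Phase 2, Section 5.3.5 says "Definitions of DLT will be as described in Section 5.3.3" but gives no DLT count. The only numeric rule attached to the 11 subjects is the response rule in Section 11.1.

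**The concern.** Tables 6 and 7 are both attributed to the proposed escalation scheme, yet they print different probabilities. If one rule governs the whole trial, both cannot describe it. If a second rule governs the step to 160 mg TID, it is not written anywhere.

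At stake is whether the printed chance of taking this step describes the design that the text sets out. The step raises the daily dose from 200 mg (2 × 100) to 480 mg (3 × 160), a factor of 2.4. It also leaves open how DLTs in the eight Stage 2 subjects bear on the decision.

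**Working it through.** **Inputs.** The rule comes from Section 5.3.2, the printed probabilities from Tables 6 and 7, and the group sizes (3 in Stage 1 and 8 in Stage 2 at 100 mg BID) from Sections 3.3.1 and 11.1. Let p be the true DLT rate, with subjects independent. The calculation concerns DLTs only and sets the response rule aside.

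**Step 1: the written 3+3.** P(escalate) = P(0/3) + P(1/3) × P(0/3). At 20%: 0.512 + 0.384 × 0.512 = 0.709.

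**Step 2: what Table 7 matches.** A search over single-stage rules (2 to 39 subjects) and two-stage rules (up to 20 subjects in total) found one rule within 0.012 of all six values. It escalates on 0/3; on 1/3 it looks at eight more subjects and escalates if at most two have a DLT. P(escalate) = P(0/3) + P(1/3) × P(≤2 of 8). At 20%: 0.512 + 0.384 × 0.797 = 0.818.

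| True DLT | P(0/3) | P(1/3) | P(≤2 of 8) | Written 3+3 | Table 6 | Inferred 3+8 rule | Table 7 |
|---|---|---|---|---|---|---|---|
| 10% | 0.729 | 0.243 | 0.962 | 0.906 | 0.91 | 0.963 | 0.96 |
| 20% | 0.512 | 0.384 | 0.797 | 0.709 | 0.71 | 0.818 | 0.82 |
| 30% | 0.343 | 0.441 | 0.552 | 0.494 | 0.49 | 0.586 | 0.59 |
| 40% | 0.216 | 0.432 | 0.315 | 0.309 | 0.31 | 0.352 | 0.35 |
| 50% | 0.125 | 0.375 | 0.145 | 0.172 | 0.17 | 0.179 | 0.18 |
| 60% | 0.064 | 0.288 | 0.050 | 0.082 | 0.08 | 0.078 | 0.08 |

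The written rule reproduces Table 6 in every row. The inferred rule reproduces Table 7 in every row. The two rules share the 0/3 term, so the whole gap lies in the 1/3 branch.

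**Step 3: Stage 2 DLTs after 0/3.** Trying every cap on DLTs among the eight after 0/3, 1/3 and 2/3, Table 7 fits only if 0/3 carries no limit (or a cap of 7, which gives the same rounded values), 1/3 carries a cap of 2, and 2/3 stops. So Table 7 in effect gives the eight Stage 2 subjects no say after 0/3.

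**Step 4: other readings of the text.** Two criteria that count all 11 subjects can be drawn from Section 5.3.2:

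- At most 3/11 (27.3%, under 33.3%; 4/11 would be 36.4%), with ≥2/3 in Stage 1 still stopping: P(0/3) × P(≤3 of 8) + P(1/3) × P(≤2 of 8). At 20%: 0.512 × 0.944 + 0.384 × 0.797 = 0.789.
- At most 1/11, applying the two-or-more bullet literally to all 11: P(≤1 of 11).

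| True DLT | Table 7 minus 3+3 | ≤3/11, ≥2/3 stops | ≤1/11 | P(0/3) × P(≥4 of 8) |
|---|---|---|---|---|
| 10% | +0.054 | 0.959 | 0.697 | 0.004 |
| 20% | +0.111 | 0.789 | 0.322 | 0.029 |
| 30% | +0.096 | 0.520 | 0.113 | 0.067 |
| 40% | +0.041 | 0.265 | 0.030 | 0.088 |
| 50% | +0.008 | 0.100 | 0.006 | 0.080 |
| 60% | −0.002 | 0.025 | 0.001 | 0.053 |

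The first column takes the printed Table 7 value minus the unrounded 3+3 value. Neither criterion gives Table 7. The last column is the chance of a path with 0/3 in Stage 1 and then at least four DLTs among the eight.

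**The case against.** Table 7 is exact for a rule that uses the 3 + 8 subjects actually planned at 100 mg BID. The captions also separate the tables by scope, within a stage and between stages, so different numbers could be intended. This stands: the fault is an omitted rule and not an arithmetic error, and a reader who infers a miscalculation would be wrong. But the caption does not supply the rule, and Section 5.3.2, which covers the whole study, prescribes something else after 1/3.

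The practical effect is also limited. High at 20% and low at 50% remain fair descriptions, the tables differ by at most 0.01 at 50% and 60%, and nothing in the documents rests the choice of 160 mg TID on Table 7. All of this stands.

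A reader might go further and infer that nothing would stop escalation after heavy toxicity in Stage 2. The documents do not support that:

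- Read literally, the two-or-more bullet bars escalation at 4/11.
- A rate of 36.4% exceeds the 33.3% gloss, although the gloss is worded for the Stage 1 MTD.
- Three roles must agree on the safety data before any escalation.
- 160 mg TID opens with its own cohort of 3 to 6 subjects and DLT rule, with fallbacks to 120 mg TID and 100 mg BID.
- The joint chance of 0/3 followed by at least four DLTs among the eight never exceeds 0.088.

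What remains is that the bullet and the gloss lead to different limits for 11 subjects, and Table 7 uses neither.

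**Conclusion.** The point holds as a mismatch between rule and table. Measured against the only written scheme, Table 7 overstates the chance of escalating to 160 mg TID by about 0.05, 0.11, 0.10 and 0.04 at true DLT rates of 10% to 40%, and by almost nothing at 50% and 60%. The rule that reproduces it is inferred from its six values; it conflicts with Section 5.3.2 after 1/3 and ignores Stage 2 DLTs after 0/3. How the two-or-more bullet and the 33.3% gloss apply to the combined 11 subjects is unclear.

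The figures assume independent DLTs at a common rate. Enrolment of exactly three subjects at 100 mg BID in Stage 1 suggests 0/3 there, but the documents do not give the count, so whether the gap affected the actual decision is unknown. No efficacy test or sample size is affected.

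**What to change.** Make rule and table agree, in one of two ways.

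1. If the written 3+3 governs this step, replace Table 7 with 0.91/0.71/0.49/0.31/0.17/0.08 and change its two sentences to 0.71 at 20% and 0.17 at 50%. These values take no account of the eight Stage 2 subjects.
2. If another criterion was used, state it in Section 5.3.2, including how the eight Stage 2 subjects count after 0/3 and how the two-or-more bullet applies to 11 subjects. Then recompute Table 7 and its two sentences.

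Under the second route the threshold is the sponsor's choice. A cap of 3/11 with ≥2/3 still stopping is in line with the 33.3% figure and gives 0.96/0.79/0.52/0.26/0.10/0.03 (from unrounded 0.2646 at 40% and 0.0255 at 60%). The literal ≤1/11 is stricter and gives 0.70/0.32/0.11/0.03/0.01/0.00. The trade-off is plain: at 40% true DLT the chance of escalating is 0.26 against 0.03, and at 20% it is 0.79 against 0.32.

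Either way, because the 11 subjects are already enrolled, report their first-cycle DLT count and say whether the criterion was fixed before that count was known.

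The cost is one table and two sentences in Section 11.1 and, for the second route, one rule in Section 5.3.2. It needs no extra subjects or procedures.

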### **3.3 Number of Subjects to be Enrolled**

- 3.3.1 Three to 38 evaluable subjects will be enrolled. In Stage 1, three successive cohorts of three subjects have been enrolled at each of the following dose levels: 40 mg/dose BID, 80 mg/dose BID, and 100 mg/dose BID. An additional eight subjects have been enrolled in Stage 2 at the highest safely tolerated dose (e.g., 100 mg/dose BID) established in Stage 1 to better define the safety, antitumor activity, and biological activities of PTC299 at this dose level. Dose escalation will continue in Stage 3 for two additional successive cohorts of 3 to 6 subjects at the following dose levels: 160 mg/dose TID and 200 mg/dose TID. Once the safety profile at each level has been established based on first cycle dose-limiting toxicities (DLTs), an additional 9 to 12 subjects will be enrolled at the highest safely tolerated dose (e.g., 200 mg/dose TID) for a total number of 15 subjects at this dose level. If the dose level of 200 mg/dose TID is not well tolerated (i.e.,  $\geq 2/6$  subjects experience a first-cycle DLT), an additional 9 to 12 subjects will be enrolled at the dose level of 160 mg/dose TID for a

total number of 15 subjects at the MTD. If the dose level of 160 mg/dose TID is not well tolerated in the initial cohort (e.g.,  $\geq 2/3$  or  $\geq 2/6$  subjects experience a first-cycle DLT), 3 to 15 subjects will be enrolled at the dose level of 120 mg/dose TID. If the dose level of 120 mg/dose TID is not well tolerated (e.g.,  $\geq 2/3$  or  $\geq 2/6$  subjects experience a first-cycle DLT), a total of 9 to 15 subjects will be enrolled at the 100 mg/dose BID dose level in Stage 3. Collectively, up to 21 patients will be enrolled in Stage 3.

- 3.3.2 Estimated accrual rate: four subjects per month.

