In Stage 3, a minimum of 12 patients will be treated at the maximally treated dose. If the underlying response rate is no greater than 10%, then the probability of observing 4 or more responses among 12 patients will be  $< 5\%$ . Thus, if there are 4 or more responses among 12 patients, it can be inferred that the response rate is  $> 10\%$ .

The minimum number of subjects to be entered in the study is **three** (i.e., if  $\geq$  two subjects experience DLT at the lowest dose level in Stage 1).

The maximum number of evaluable subjects to be enrolled in the study is **38** (i.e., 9 subjects have been enrolled into Stage 1, 8 subjects have been enrolled into Stage 2, and up to 21 subjects will be enrolled to Stage 3). Assuming that  $\sim 15\%$  of subjects will not be evaluable for response, we estimate that the maximum number of subjects in the study will be **44**.

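### The dose-specific activity cutoff in Section 11.1 is set for 12 subjects; Section 3.3.1 plans 15, where no cutoff is stated and 4 or more carries a 5.6% error, and the stated minimum of 12 conflicts with a fallback of 9 to 15

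*Combined protocol and SAP*

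**What the plan says.** Section 11.1 (Design and Sample Size) contains two efficacy statements.

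- The formal one rejects a response rate of 10% or less if at least 6 subjects respond by the end of Stage 3, and concludes that further investigation is warranted.
- The second concerns the selected dose only. It opens with "In Stage 3, a minimum of 12 patients will be treated at the maximally treated dose", says that 4 or more responses among 12 would occur with probability below 5% if the true rate were no more than 10%, and concludes: "Thus, if there are 4 or more responses among 12 patients, it can be inferred that the response rate is" above 10%.

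Section 3.3.1 gives the enrolment numbers.

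- **Main path:** after an initial cohort of 3 to 6, "an additional 9 to 12 subjects will be enrolled at the highest safely tolerated dose", "for a total number of 15 subjects at this dose level". The same total of 15 applies if 160 mg/dose TID turns out to be the MTD.
- **First fallback:** "3 to 15 subjects will be enrolled at the dose level of 120 mg/dose TID".
- **Second fallback:** "a total of 9 to 15 subjects will be enrolled at the 100 mg/dose BID dose level in Stage 3".
- **Cap:** Stage 3 as a whole takes at most 21.

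Section 11.2 estimates the response rate with a 95% confidence interval and also states its precision (no wider than ±28.3%) for 12 patients.

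**The concern.** The only threshold specific to the selected dose is written for a sample size that the enrolment section does not plan. At the end of the trial the analyst will most likely have 15 subjects at that dose and a rule for 12. A result of exactly 4 of 15 could then be read in three ways: as positive, by carrying over the cutoff; as negative, by requiring 5; or according to how many responders fell among the first 12. The choice could be made after the data are seen. Such a result is not remote: at a true rate of 35%, the alternative used in Section 11.1, it has a probability of about 18%.

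Separately, both the rule and the precision statement lean on a minimum of 12 that the enrolment rules do not guarantee.

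**Working it through.** **Inputs.** Null rate 10%, cutoff 4, n = 12 and stated error below 5% (Section 11.1). Alternative rate 35% (Section 11.1, Phase 2 hypotheses). Planned n = 15, fallback 9 to 15, Stage 3 cap 21 (Section 3.3.1).

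**Formula.** For X binomial(n, p), P(X ≥ r) = 1 − Σ C(n,k) p^k (1−p)^(n−k), summed over k = 0 to r−1. The error uses p = 0.10 and the power uses p = 0.35.

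**Step 1: the plan's own figure.** n = 12, r = 4, p = 0.10: 1 − (0.28243 + 0.37657 + 0.23013 + 0.08523) = 1 − 0.97436 = 0.0256. The statement of below 5% is reproduced.

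**Step 2: the planned size.** The build-up is 3 + 12 or 6 + 9, each giving 15. n = 15, r = 4, p = 0.10: 1 − (0.205891 + 0.343152 + 0.266896 + 0.128505) = 1 − 0.944444 = 0.0556.

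**Step 3: other sizes and cutoffs.**

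| n | Cutoff | Error at 10% | Power at 35% |
|---|---|---|---|
| 9 | ≥3 | 0.0530 | 0.663 |
| 9 | ≥4 | 0.0083 | 0.391 |
| 12 | ≥4 | 0.0256 | 0.653 |
| 13 | ≥4 | 0.0342 | 0.722 |
| 14 | ≥4 | 0.0441 | 0.780 |
| 15 | ≥4 | 0.0556 | 0.827 |
| 15 | ≥5 | 0.0127 | 0.648 |

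From 9 to 14 subjects, 4 is the smallest cutoff with error below 5%: a cutoff of 3 already gives 5.3% at 9, and its error rises with n. At 15 the smallest is 5. The probability of exactly 4 of 15 at a 35% rate is 0.827 − 0.648 = 0.179.

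**Step 4: the minimum of 12.** If 160 mg/dose TID and 120 mg/dose TID each use 6 subjects, 21 − 6 − 6 = 9 remain for 100 mg/dose BID, which matches the lower end of the stated range. On that path 12 cannot be reached: 6 + 6 + 12 = 24 exceeds 21, and 9 + 8 + 24 = 41 exceeds the study maximum of 38 evaluable subjects. The precision statement is affected too: 1.96 × √(0.25/12) = 0.283 reproduces ±28.3%, but at 9 the same formula gives 0.327.

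**The case against.** **No stated number is wrong.** The sentence names its denominator, and at 12 its claim is true. A reader might infer that the plan asserts a false error rate. It does not: 5.6% arises only if someone carries the cutoff of 4 to 15, which the documents never do. This stands. The defect is a missing cutoff for the planned size.

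**It is not the go-forward rule.** A reader might take 4 of 12 as the decision on whether the drug proceeds. That role belongs to the rule of at least 6 responders at the end of Stage 3. The primary objective is to estimate the response rate (Section 2.1.3), and the interval in Section 11.2 can be computed at any n. This also stands: the sentence is a supporting inference, though it is the only one tied to the selected dose.

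**Fewer than 15 may be analysed.** Section 11.1 assumes about 15% of subjects are not evaluable for response, and 15 × 0.85 = 12.75. At 12 or 13 the cutoff holds. Replacement under Section 3.3.3 depends on completing cycle 1 and on DLT evaluation, not on response. Against this, Sections 3.3.1 and 11.1 describe the total of 38, which includes the 21 of Stage 3, as evaluable. Fifteen evaluable subjects is the more natural reading, but the text does not settle it.

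**The fallback sizes.** It is tempting to say that the fallback of 9 breaks the error rate or leaves only 39% power. Neither follows. The error at 9 is 0.8%. Section 11.1 already counts 11 subjects at 100 mg/dose BID from the earlier stages, so 9 more would give 20 at that dose; the plan does not say whether they are pooled for this inference. The lower end of 3 for 120 mg/dose TID appears to be an initial cohort at a level that is not tolerated, so it is not a clear breach of the minimum.

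**Conclusion.** The point holds as a mismatch between Sections 11.1 and 3.3.1. The stated rule is right for 12 subjects and remains below 5% through 14. At the planned 15 no cutoff is given, and carrying over 4 would exceed 5% by 0.56 percentage points. This affects the conclusion only if exactly 4 of 15 respond. The minimum of 12 contradicts the 9 to 15 allowed in the 100 mg/dose BID fallback; that is a conflict of text, not of error rate.

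The 5.6% figure assumes 15 evaluable subjects at the selected dose, a one-sided exact binomial test against 10%, and no pooling with earlier stages. The effect is modest, but the correction should be made before the data at that dose are read, because the alternative readings disagree on a plausible result.

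**What to change.** In Section 11.1, choose one of these and state it in advance:

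1. Give the cutoff by the number of evaluable subjects analysed at the dose: 4 or more for up to 14, and 5 or more for 15. At 15 this has error 1.3% and power 65% at a 35% rate.
2. Keep 4 or more of 15 and state the one-sided error as 5.6%. Power is 83%.
3. Apply the 4-of-12 rule to the first 12 evaluable subjects (error 2.6%, power 65%), with all subjects contributing to the estimate and interval.

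Then add three clarifications: how this inference relates to the formal rule of at least 6 responders; whether the 11 earlier subjects at 100 mg/dose BID are pooled in the fallback, since the cutoffs above assume they are not; and a corrected minimum that matches Section 3.3.1. The precision statement in Section 11.2 should be checked against the corrected minimum. Raising the fallback in Section 3.3.1 to 12 is not a workable alternative, because it would exceed the Stage 3 cap of 21 when both higher cohorts use 6 subjects.

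The cost is a few sentences, with no added subjects or procedures. Option 1 gives up 18 points of power at 15 relative to option 2 (83% against 65%); option 2 accepts a stated error slightly above 5%.
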